## **Implementation of HIV Pre-Exposure Prophylaxis (PrEP) among People Who Inject Drugs (PWID) in Ukraine**

### **LIST OF ABBREVIATIONS AND ACRONYMS**

ACTG	AIDS Clinical Trials Group
AE	Adverse Event
AIDS	Acquired Immunodeficiency Syndrome
ALT	Alanine transaminase
ART	Antiretroviral Therapy
ARV	Antiretroviral
AST	Aspartate transaminase
BUN	Blood Urea Nitrogen
CBC	Complete Blood Count
CBO	Community Based Organization
CCMT	Care Coordination Measurement Tool
CI	Confidence Interval
CPCQ	Client Perception of Coordination Questionnaire
CPK	Creatine phosphokinase
CPQA	Clinical Pharmacology Quality Assurance
CQR	Consensual Qualitative Research Method
CRF	Case Report Form
CTM	Care Transition Measure
DBS	Dried Blood Spot
EAE	Expedited Adverse Event
FTC	Emtricitabine
FTC/TDF	Emtricitabine/ Tenofovir Disoproxil Fumarate FTC-TP Emtricitabine Triphosphate
HCCQ	Health Care Climate Questionnaire
HIV	Human Immunodeficiency Virus
ICF	Informed Consent Form
IRB	Institutional Review Board
MD	Medical Doctor
NIH	(United States) National Institutes of Health
PHC	Public Health Center

## PrEP for PWID in Ukraine

PLHIV	People Living with HIV
PrEP	Pre-Exposure Prophylaxis
QA/QC	Quality Assurance/ Quality Control
RNA	Ribonucleic Acid
SA	Substance Abuse
SAE	Serious Adverse Event
SDT	Self-Determination Theory
SOP	Standard Operating Procedure
STD	Sexually Transmitted Disease
STI	Sexually transmitted infection
SUSAR	Suspected Unexpected Serious Adverse Reaction
SW	Social Worker
TB	Tuberculosis
TDF	Tenofovir Disoproxil Fumarate
TFV	Tenofovir
TFV-DP	Tenophovir Diphosphate
TSRQ	Treatment Self-Regulation Questionnaire

## Implementation of HIV Pre-Exposure Prophylaxis (PrEP) among People Who Inject Drugs (PWID) in Ukraine

### SCHEMA

Purpose:	To assess the acceptability and feasibility of PrEP for People Who Inject Drugs (PWID) in Kyiv, Ukraine with and without SMS facilitation.
Design:	An 24-week prospective randomized controlled trial of PrEP as usual versus PrEP with SMS facilitation
Population:	HIV-uninfected PWID at risk for HIV infection in Kyiv, Ukraine.
Study Size:	A total of 200 participants randomized 1:1 to experimental and control arms.
Study Regimen:	All participants will be offered once daily oral emtricitabine 200 mg / tenofovir disoproxil fumarate 300 mg (FTC/TDF) combined with SMS facilitation in the experimental arm.
Study Duration:	12 months including closeout activities. Preparatory phase is planned to take 2 months. Recruitment is anticipated to take place over a 2-month period. Each participant will be followed for a total of 6 months. Two months are included for data clean-up and closeout.
Primary Objectives:	To compare adherence to and persistence on daily PrEP prescribed as the fixed dose formulation to PWID randomized 1:1 to PrEP as usual or SMS-enhanced PrEP.
Secondary Objectives:	

 To describe patterns and attributes of PrEP adherence among participants (e.g., SMS intervention acceptance, substance use, sociocultural factors)

 To measure changes in injection and sexual risk taking behavior among study participants

 To describe client- and provider-level barriers to PrEP initiation and adherence

Study Sites:	

 Institute of Epidemiology and Infectious Diseases (Lavra) Clinic

 Club Eney Community Center

---

## 1.0 INTRODUCTION

### 1.1 Background and Prior Research

After a long decline, HIV epidemic among PWID in Ukraine is again showing signs of growth. In the two last rounds of national IBBS, prevalence in young PWID and overall is increasing. Needle and syringe programs (NSP) are a key strategy to prevent HIV among PWID, and Ukraine has reached the recommended level of coverage of 60%. It is evident that substantial increase in frequency of coverage is not feasible for a large number of PWID. Availability of opioid agonist therapy (OAT) also remains suboptimal at 4% of those with opioid dependence. Pre-exposure prophylaxis (PrEP) is a potential strategy to fill the gap in the prevention continuum for PWID in Ukraine and countries with similar epidemics.

PrEP with tenofovir/emtricitibine (TDF/FTC) is an evidence-based HIV prevention strategy recommended for key populations where HIV incidence exceeds 1%. In RCTs, it is effective in both men-who-have-sex (MSM) and people who inject drugs (PWID). PrEP administered *daily* with TDF/FTC was approved by the FDA with CDC and WHO providing guidance on its use in MSM in 2012, and in PWID in 2014. PrEP uptake, however, in these highest-risk subpopulations of MSM and PWIDs is low, and adherence to the daily medication regimen is the greatest barrier to scale-up for those who need it most.

PrEP efficacy in both MSM and PWID in RCTs reduces HIV transmission by ~50%. Adherence, however, is the key factor contributing to its success. For example, in the IPrEx study in MSM, self-reported adherence was 51%, though dried blood testing (DBS) suggested it as being only 41%. Similarly, in the Bangkok Tenofovir Study (BTS), self-reported adherence was 67%, though daily supervised monitoring confirmed only 49% adherence. In the BTS, an open-label extension of 793 PWID, showed low overall adherence to daily PrEP; almost half (47%) had less than 10% adherence, but only 25% had high (>90%) adherence. PrEP in the BTS was supervised daily at methadone clinics and during incarceration, and being incarcerated was independently associated with higher levels of adherence, suggesting that without daily monitoring, PrEP adherence in the community will likely be lower. Moreover, subsets of MSM in PrEP trials had underlying substance use disorders, yet the efficacy of PrEP or adherence levels among them is unknown. In the BTS, all PWID on the trial were maintained on methadone and the analysis did not disaggregate efficacy or adherence for the subgroup that continued to inject. Consequently, it is crucial to better understand adherence to daily PrEP in subgroups of MSM and PWID with substance use disorders who have suboptimal adherence to PrEP, but who are the ones who likely need it most.

Adherence guidelines by the International Association of Physicians in AIDS Care describes adherence optimization strategies, including in key populations like patients with substance use disorders. Though these guidelines do not include PrEP, recommendations for PrEP adherence are likely to apply. Short-messaging service (SMS) or text messaging is recommended, including from a systematic review of reviews that supports SMS use and recommends refinements in frequency and message content. Another systematic review in patients with HIV confirmed the adherence benefits from using SMS and extended it to improvements in clinic attendance, which is crucial for PrEP monitoring every three months. Moreover, while SMS works generally, two-way interactive and tailored reminders appear to be most beneficial, but can be burdensome to patients if too frequent.

A survey of 400 PWID receiving chronic methadone maintenance assessed their ownership and usage frequency of various communication technologies, including cell phones and smart phones, and their acceptance of SMS. Of these, 67% were still using drugs (mostly cocaine). Overall, 91.5% regularly used some form of cell phone with most (71.3%) of these having a smart phone. Over one third (35.2%) of participants had evidence of moderate to severe neurocognitive impairment, which is associated with lower adherence levels. Reminders, including the use of SMS, is an integral strategy for addressing medication adherence in individuals with neurocognitive impairment. High levels (72.3%) of interest were expressed for communicating using SMS, and was higher among those with neurocognitive impairment.

An ongoing study to optimize medication adherence in HIV patients with cocaine use disorders used formative research to establish the procedures for monitoring adherence and tailoring the reminder messages using focus groups and beta testing. Integral to the SMS reminders is the frequency (patients indicated daily was optimal), the timing of the reminder (they wanted to set their own time of the day),

content (they preferred positive message frames that did not allude to HIV), and quantity (one additional reminder after the preferred time and they would like to set the delay in the reminder from 15 to 60 minutes).

## 1.2 Rationale

The proposed study is significant in that PWID contribute a significant proportion to ongoing HIV transmission in Ukraine, and little is known about possible adherence levels to PrEP. Moreover, given the documented challenges with medication adherence in active drug users, evidence-based and low cost strategies to optimize medication are urgently needed if PrEP is to be effective in this key population. The proposed study is innovative in that it uses an RCT design testing a promising adherence enhancement approach, and focuses on a target population of active drug users who were not fully examined for either efficacy or adherence in prior trials.

## 1.3 Participating Sites

The study is designed to evaluate PrEP adherence in the population at greatest risk for HIV acquisition in Ukraine, PWID. We will achieve efficiencies by situating the PrEP provision model within real-world community settings and draw on the expertise of clinicians that have already demonstrated expertise in working with PWID and other populations at high risk of HIV. Sites located in various parts of Kyiv and run by NGOs currently providing HIV prevention services to PWID were chosen due to their excellent access to the target group and experience in provision of various social and para-clinical services. The primary community sites will partner with HIV clinical facilities to enable necessary laboratory testing and medication provision.

## 1.4 HIV Seroconversion

Incident HIV infections on this study are expected to occur uncommonly, even in the at-risk study population. However, any participant experiencing an incident HIV infection offers the opportunity to assess the impact of the PrEP regimen. Consequently, these participants will discontinue study medication and will be carefully characterized with regard to their HIV RNA level, CD4 cell count and set points over time, as well as antiretroviral drug resistance, and other factors.

## 2.0 STUDY OBJECTIVES AND DESIGN

### 2.1 Primary Objectives

- To compare adherence to and retention on daily PrEP prescribed as the fixed dose formulation to PWID randomized 1:1 to PrEP as usual or SMS-enhanced PrEP.

### 2.2 Secondary Objectives

- To describe patterns and attributes of PrEP adherence among participants (e.g., SMS acceptance, substance use, sociocultural factors)
- To measure changes in injection and sexual risk taking behavior among study participants
- To describe client- and provider-level barriers to PrEP initiation and adherence

### 2.3 Study Design (Quantitative Component)

The study is a hybrid type 2 implementation design at two sites partnering with local healthcare facilities. In a prospective randomized controlled trial, participants will be randomized 1:1 to PrEP prescribed as usual or PrEP with SMS adherence facilitation.

Participants will be followed up for up to 6 months after enrollment and will be assessed every month for key PrEP adherence measures.

### 2.4 Study Design (Qualitative Component)

The primary objective of the qualitative component is to provide a contextual understanding of the multi-

level barriers and facilitators in the initiation, acceptability, and adherence to PrEP for PWID. The qualitative data will provide relevant findings regarding the participants' overall impressions and experiences related to their study participation, including motivations for participating in the study, perceptions about PrEP, reasons that PWID choose to initiate or decline PrEP, and describing the most helpful and least helpful components of study/service uptake for PrEP provided in this study (e.g., experimental services provided such as SMS facilitation). The qualitative component will also describe the individual, cultural, institutional, and geographic-specific barriers and facilitators that influence PWID initiation, utilization and adherence to PrEP, including those critical factors that influence study participation and up-take of PrEP (e.g., substance use, socio-economic indicators, culturally specific psychosocial stressors related to stigma). Importantly, the study will also assess the providers' perspectives on PrEP utilization among PWID, and system-level barriers.

### 3.0 STUDY POPULATION

The study will enroll 200 eligible HIV-uninfected PWID, 100 at each site. Participants will be selected for the study according to the criteria specified below. They will be recruited, screened and enrolled as described in Section 3.3. Issues related to participant retention and withdrawals from the study are described in Sections 3.4 and 3.5, respectively.

#### 3.1 Inclusion Criteria

Individuals who meet all of the following criteria are eligible for inclusion in this study:

- 18 years of age or older
- No prior HIV diagnosis (self-report)
- Recent injecting drug use, defined as self-report of any type of drug injection and presence of visible injection marks verified by recruiting staff
- Able and willing to sign the informed consent, assessed by consenting staff
- Willing to provide locator information in accordance with the Study Operating Procedures (SOP)
- Have a mobile phone able to receive short messages (SMS).

#### 3.2 Exclusion Criteria

PWID who meet any of the following criteria will be excluded from this study:

- Any reactive or positive HIV test at Screening
- Any reactive or positive HBsAg test at Screening
- Serum creatinine < upper limit of normal (ULN) and calculated creatinine clearance of at least 60 mL/min by the Cockcroft-Gault formula where:
  - $eCcr \text{ in mL/min} = [(140 - \text{age in years}) \times (\text{actual body weight in kg})] / (72 \times \text{serum creatinine in mg/dL})$
- Planning to move out of the area or to travel for more than 3 months during the study follow-up period
- Unwilling to adhere to study procedures
- Use of ARV drugs (PrEP or PEP) in the last 60 days prior to anticipated enrollment by self-report
- Prior history of a gastrectomy, colostomy, ileostomy, or any other procedure altering the gastrointestinal tract or drug absorption (provided by self-report, or obtained from medical history or records)
- Any condition, that in the opinion of study staff, would make participation in the study unsafe, or interfere with achieving the study objective

Any person who cannot provide informed consent will be excluded from participation in the project. Staff conducting screening will be trained to identify participants who cannot provide appropriate informed consent. If it is determined that the inability to provide informed consent is due to a temporary/situational factor (e.g., intoxication), these persons will be given the opportunity to reschedule their enrollment appointment as appropriate. All participants will be afforded the same protections.

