## **5.0 STUDY PROCEDURES**

An overview of the study visits and procedures schedule is presented in Appendix I and has been written in concordance with current WHO guidelines for PrEP administration. In addition, all providers will be required to follow MOH requirements for the initiation of Tenof-EM for PrEP. Presented below is additional information on visit-specific study procedures. Detailed instructions to guide and standardize all study procedures across sites will be provided in the SOPs.

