
9. PrEP Navigation and study product supply

After the brief PrEP discussion, PNs will ensure that each study participant has received the first supply of the medication for one month.

10. SMS reminder customization

The experimental group participants will complete a SMS customization tool, setting key parameters for the intervention (frequency, timing, wording).

11. SMS reminder test

After setting the SMS intervention parameters, a sample message will be delivered to the participant to test the procedure.

12. HIV/ STI behavioral risk-reduction counseling, provision of prevention supplies

Brief risk reduction counseling will be provided to all participants at each visit. These counseling sessions will reinforce the role of consistent use of clean syringes and condoms in HIV/STI prevention, as well as other strategies such as addiction treatment. The overall goal will be to supplement PrEP counseling by supporting participants to adopt or continue risk-reduction practices. Prevention supplies, including clean syringes and condoms will be offered at each visit. Participants will be also provided with information about opioid agonist treatments, and referred to the preferred clinic if necessary.

*Clinical Evaluations/ Procedures (clinical staff)*

13. Medical history including but not limited to co-morbidities, concomitant medications, HIV risk history

The clinician will evaluate medical history of the participant to verify the absence of potential contraindications and drug interactions for PrEP.

14. Symptom-driven physical exam

If any physical or mental symptoms will be expressed by the participant, the clinician will conduct an exam to diagnose the condition and provide appropriate referrals if needed.

Laboratory Evaluations/Procedures (clinical staff)

15. HIV testing

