HIV testing will be conducted according to the current HIV testing guidelines by trained staff, with pre- and post-test counseling. According to Ukrainian legislature, HIV diagnosis cannot be made at any setting other than an accredited governmental HIV lab. Therefore, a positive result of rapid testing (regardless of the number of confirmatory runs) will be explained to a subject as preliminary and insufficient to definitively confirm HIV infection, which can be done at specialized health care institutions. As specified in the National HTC guidelines, post-test counseling will provide all details on where the confirmatory testing can be done, and appropriate referrals will be provided.

Participants who test HIV positive will be withdrawn from the study at this point.

16. HBsAg testing

Testing for Hepatitis B is needed because the drugs used in Tenof-EM® can also be used to treat hepatitis B virus and taking Tenof-EM® now might result in less effective treatments for hepatitis B. Testing will be done using a venous blood sample with test kits available at the clinic. Participants positive for HBsAg will be excluded from the study and will be provided appropriate counseling.

17. Blood collection for creatinine test with subsequent calculation of creatinine clearance

To verify eligibility, participants will provide a venous blood sample for the creatinine test. Routinely, the test results will be available within 3 days. Considering the low expected prevalence of elevated creatinine levels, PrEP will be dispensed at the same visit before the creatinine test result is available. If an elevated level is detected, the participant will be contacted, instructed to discontinue PrEP medication and invited for an interim visit to the clinician for a thorough assessment of renal function and possible reasons for elevated creatinine.

18. DBS storage for pharmacology testing

DBS samples will be processed and stored for all participants; testing may be limited to a subset of these samples. DBS will be stored at -20° C within 24 hours of collection and shipped in bulk to a centralized laboratory on dry ice for testing. TDF will be quantified with a validated liquid chromatography tandem mass spectrometry method.

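### The renal item in Protocol 3.2 excludes people with normal kidney function, the reverse of what 5.2 item 17 and 6.6.3 require

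*Protocol*

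**What the plan says.** Protocol 3.2 opens its list with "PWID who meet any of the following criteria will be excluded from this study". Meeting a single item is therefore enough for exclusion. The renal item reads "Serum creatinine < upper limit of normal (ULN) and calculated creatinine clearance of at least 60 mL/min by the Cockcroft-Gault formula", followed by the Cockcroft-Gault formula. Section 3.1 (Inclusion Criteria) has no renal item.

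Elsewhere the protocol runs the other way:

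- **Section 5.2, item 17** gives the purpose of the test: "To verify eligibility, participants will provide a venous blood sample for the creatinine test". It then says "Considering the low expected prevalence of elevated creatinine levels, PrEP will be dispensed at the same visit before the creatinine test result is available", and "If an elevated level is detected, the participant will be contacted, instructed to discontinue PrEP medication". No numerical cut-off is given for an elevated level.
- **Section 6.6.3** requires drug to be stopped temporarily when a clearance below 60 mL/min is confirmed, and lets the investigator restart it when re-testing gives 60 mL/min or more.
- **Section 5.6** asks for creatinine and clearance again before PrEP is restarted, as a check of eligibility against the screening parameters, but states no threshold.

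**The concern.** The sentence reads as an inclusion criterion that was placed in the exclusion list without being negated. Taken literally, it turns away almost the whole target population and does not itself exclude people with impaired renal function.

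Three things make this more than a cosmetic slip:

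- It sets the entry rule for a drug that the protocol itself withholds at low clearance.
- Neither 5.3 nor Appendix I schedules a creatinine test after Enrollment, so this rule governs the only routinely scheduled renal check.
- Section 8.6 requires all protocol deviations to be documented and reported. Judged literally against 3.2, nearly every properly enrolled participant would be one.

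**Working it through.** The protocol states no result to reproduce here. The check applies its own formula to assumed people and compares three versions of the rule.

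**Inputs from the protocol.** Formula (3.2): clearance in mL/min = (140 − age) × weight in kg / (72 × serum creatinine in mg/dL). Clearance threshold: 60 mL/min (3.2 and 6.6.3).

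**Assumptions.** The ages, weights and creatinine values are illustrative. The protocol gives no value for ULN, so 1.1 to 1.3 mg/dL is assumed; every classification below is the same across that range. An elevated level in item 17 is taken to mean creatinine at or above ULN, because item 17 names no cut-off.

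**Clearances.**

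1. Age 35, 70 kg, creatinine 0.9: (105 × 70) / (72 × 0.9) = 7350 / 64.8 = 113.4
2. Age 35, 70 kg, creatinine 2.0: 7350 / 144 = 51.0
3. Age 65, 45 kg, creatinine 1.0: (75 × 45) / (72 × 1.0) = 3375 / 72 = 46.9
4. Age 35, 70 kg, creatinine 1.5: 7350 / 108 = 68.1

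**Classification by this item alone.**

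| Case | Creatinine vs ULN | Clearance | 3.2 as printed | Signs reversed, *and* kept | Signs reversed, *or* |
|---|---|---|---|---|---|
| 1 | below | 113.4 | excluded | not excluded | not excluded |
| 2 | above | 51.0 | not excluded | excluded | excluded |
| 3 | below | 46.9 | not excluded | not excluded | excluded |
| 4 | above | 68.1 | not excluded | not excluded | excluded |

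As printed, the item excludes only the person with normal function. Section 6.6.3 would stop drug in cases 2 and 3, and item 17, read as above, would stop it in cases 2 and 4. The printed rule excludes none of these three.

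**Why the connecting word matters.** The negation of (creatinine < ULN and clearance ≥ 60) is (creatinine ≥ ULN or clearance < 60). Creatinine at which clearance equals 60 mL/min:

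- Age 35, 70 kg: 7350 / (72 × 60) = 7350 / 4320 = 1.70 mg/dL
- Age 65, 45 kg: 3375 / 4320 = 0.78 mg/dL

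With *and* kept, the younger person is missed for creatinine from ULN up to 1.70 mg/dL, and the older person is missed for creatinine above 0.78 mg/dL and below ULN.

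**The case against.** The strongest reply is that the practical consequence is close to nil. A rule that turns away nearly every candidate would be noticed at the first screening, and item 17 and 6.6.3 make the intended direction plain. Other safeguards also remain:

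- a catch-all exclusion in 3.2 ("Any condition, that in the opinion of study staff, would make participation in the study unsafe");
- the requirement in 5.0 that "all providers will be required to follow MOH requirements for the initiation of Tenof-EM for PrEP";
- the clinician's review of medical history in 5.2 item 13 ("to verify the absence of potential contraindications and drug interactions for PrEP").

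This stands, and it limits the severity. It does not make the printed criterion right, and none of the three safeguards states a renal threshold in the protocol.

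Other points also hold. The value of 60 mL/min agrees with 6.6.3, so the fault lies in the direction or placement of the item and not in the number. Section 6.6.3 governs on-study toxicity and is not an eligibility rule; it is evidence of intent. The comparison of *and* with *or* tests a possible bad correction rather than the protocol's own text, and moving the sentence to 3.1 avoids the question altogether. Finally, what happens to a participant whose creatinine result arrives after randomization is a separate matter and adds no weight to this point.

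A fault in PDF extraction is not a likely explanation: even if the less-than sign had been misread, the clearance limit is spelled out in words and points the same wrong way.

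**Conclusion.** The concern holds. This is a drafting error, but it sits in an operative eligibility and safety criterion and should be fixed. Read literally, the item excludes people with normal renal function and lets through all three illustrative people for whom 6.6.3 or item 17 would stop the drug.

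That the rule is inverted follows from the text alone. Only the worked cases depend on assumptions: the illustrative people, a ULN of 1.1 to 1.3 mg/dL, and the reading of an elevated level as at or above ULN. Sites will probably apply the rule as meant. The randomized adherence comparison and the sample size are not affected.

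**What to change.** Do one of the following:

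- Move the renal sentence and its formula unchanged from 3.2 to 3.1 Inclusion Criteria.
- Keep it in 3.2, reworded as: serum creatinine at or above ULN, **or** calculated creatinine clearance < 60 mL/min. If the sponsor means to admit people exactly at ULN, use above ULN instead.

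Two optional clarifications could go in the same edit. Section 5.6 could point to the corrected criterion, since it gives no threshold of its own. Section 5.2 item 17 could say whether a participant who then fails the criterion is excluded or followed off drug, because the result routinely takes up to 3 days while randomization and dispensing take place at the Enrollment visit.

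The cost is one line in 3.2 (or its move to 3.1) and, if the options are taken, one cross-reference and one sentence. No visits, tests or participants are added.

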#### 5.6 Initiating or Starting PrEP after the Enrollment Visit

For any participant who has not taken PrEP or PEP in the past 60 days, PrEP may be restarted at Month 3 visit, after confirming PrEP eligibility according to the following Screening Visit parameters:

- HIV testing
- HBsAg testing
- Blood collection for creatinine test with calculation of creatinine clearance

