## **6.6 Toxicity Management**

The site clinician has the discretion to hold FTC/TDF at any time if s/he feels that continued medication use would be harmful to the participant or interfere with treatment deemed clinically necessary according to the judgment of the investigator. Clinical or laboratory abnormalities that require follow up will be documented, and the research associate or clinician will contact the participant to schedule an interim visit for follow-up and/or repeat laboratory testing. All participants reporting an adverse event will be followed clinically until the occurrence resolves (returns to baseline grade, defined as grade at enrollment) or stabilizes or an effective referral to local health care providers is accomplished.

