### **6.6.2 Creatinine Elevations**

For creatinine elevations >1.5-fold above baseline creatinine (at screening), serum creatinine will be repeated as soon as possible, preferably within 7 days. Participants who fail to have a confirmed test within two weeks of receiving the initial result should be permanently discontinued from use of the study drug and the CMC should be notified. FTC/TDF will be held for confirmed creatinine elevations >1.5-fold

above baseline until creatinine returns to <1.3-fold above baseline, at which point the participant may be re-challenged with FTC/TDF after consultation with the site investigator. Clinicians may re-test creatinine levels more often (i.e., weekly) should they choose; however, after the initial re-test approximately 7 days later, it is not required per protocol to re-test serum creatinine until the next scheduled study visit. If serum creatinine rises again to >1.5-fold above baseline when drug is restarted, the CMC must be notified and FTC/TDF should be permanently discontinued and the participant will be monitored as deemed clinically appropriate in consultation with the CMC until level returns to baseline (screening value) or stabilizes.

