### 6.6.3 Creatinine Clearance

- Estimated CrCl < 60 mL/min

If the calculated creatinine clearance is <60 mL/min, it should be confirmed ideally within approximately one week of the receipt of the results.

**Discontinue study drug temporarily. Participants who fail to have a confirmed test within two weeks of receiving the initial result should be permanently discontinued from use of the study drug and the CMC should be notified.**

- Confirmed CrCl < 60 mL/min

If the calculated creatinine clearance is confirmed to be <60 mL/min, the study drug must be temporarily discontinued. As previously stated, participants who fail to have a confirmed test within two weeks of receiving the initial result should be permanently discontinued from use of the study drug and the CMC should be notified. The participant will be monitored as deemed clinically necessary in consultation with the CMC until level returns to baseline (screening value) or stabilizes.

**Temporarily discontinue study drug (unless the participant does not return for repeat testing within approximately two weeks).**

- Re-testing result is  $\geq 60$  mL/min

If re-testing yields a result  $\geq 60$  mL/min, the Investigator may re-start study drug use, and follow creatinine clearance over time as deemed clinically necessary.

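### Section 3.2 lists normal renal function as a reason for exclusion; the criterion is printed backwards and, as a minor second point, its Cockcroft-Gault formula has no female factor.

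*Protocol*

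**What the plan says.** The protocol's Section 3.2 opens with the rule "PWID who meet any of the following criteria will be excluded from this study". The third bullet under that rule is "Serum creatinine < upper limit of normal (ULN) and calculated creatinine clearance of at least 60 mL/min by the Cockcroft-Gault formula where". The equation printed beneath it is (140 − age) × actual body weight in kg, divided by 72 × serum creatinine in mg/dL. It has no term for sex, and no other section adds one.

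Three other places bear on the renal limit:

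- Section 5.2, item 17 (enrollment visit). Creatinine is drawn and clearance calculated to check eligibility, but "PrEP will be dispensed at the same visit before the creatinine test result is available". The stated follow-up is "If an elevated level is detected, the participant will be contacted, instructed to discontinue PrEP medication".
- Section 6.6.3. An estimated clearance below 60 mL/min leads to a temporary stop and a repeat test, and "If the calculated creatinine clearance is confirmed to be <60 mL/min, the study drug must be temporarily discontinued".
- Section 5.6. PrEP may be restarted at Month 3 "after confirming PrEP eligibility according to the following Screening Visit parameters", which include creatinine and clearance.

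Neither 5.6 nor 6.6.3 names a formula. Section 3.1 sets no limit on sex, and Section 3.4 refers to participants of both sexes.

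**The concern.** Every other bullet in the list is a true reason to keep someone out. The renal bullet is a condition a suitable participant should satisfy. Under the any-bullet rule it turns the criterion round, for a drug that the protocol itself stops for poor renal function. A screening form, eligibility checklist or deviation check copied from Section 3.2 would carry the error.

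The formula raises a second question. The bullet names Cockcroft-Gault, which for women carries a multiplying factor below 1. Without it, clearance in women is overstated, and some whose adjusted value is below 60 mL/min would pass even after the direction is put right.

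**Working it through.** **Step 1: direction.** Let A be creatinine below ULN and B be clearance of at least 60 mL/min.

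- As printed: excluded if A and B; not excluded by this bullet if A or B fails.
- As implied by 5.2 item 17 (elevated creatinine stops drug) and 6.6.3 (clearance below 60 stops drug): excluded if A or B fails.

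The two rules are exact complements, so the bullet as printed classifies every person the wrong way. To show scale, a simulation of women took mean age 35 to 40 (SD 8), mean weight 58 to 62 kg (SD 11), mean creatinine 0.72 to 0.80 mg/dL (SD 0.12 to 0.15) and ULN 1.0 to 1.2 mg/dL, all assumed. Between 89% and 99.8% met the printed bullet and would be excluded.

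**Step 2: the female factor, reading the bullet as intended.** The protocol gives no factor. Assume f = 0.85, with 0.80 and 0.90 as a range.

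- Overstatement without the factor: 1/f − 1 = 18% (25% at 0.80; 11% at 0.90).
- A printed 60 mL/min becomes 60 × f = 51 (48; 54).
- An adjusted 60 needs a printed 60/f = 70.6 (75.0; 66.7).

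Women with a printed value from 60 up to 70.6 (75.0; 66.7) therefore pass wrongly, provided creatinine is below ULN.

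Example: age 50, 45 kg, creatinine 0.85 mg/dL. Printed: 90 × 45 / (72 × 0.85) = 4050 / 61.2 = 66.2. Adjusted: 56.25 (52.9; 59.6). She is below 60 across the whole range of f.

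**Step 3: how far the ULN condition narrows the group.** Setting clearance to 60 gives creatinine = (140 − age) × weight / 4320. The wrong-pass band runs from f times that value up to that value or the ULN, whichever is smaller. The protocol gives no ULN; assume 1.0 mg/dL.

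| Woman | f = 0.85 | f = 0.80 | f = 0.90 |
|---|---|---|---|
| Age 50, 45 kg | 0.80–0.94 | 0.75–0.94 | 0.84–0.94 |
| Age 35, 45 kg | 0.93–1.00 | 0.88–1.00 | 0.98–1.00 |
| Age 40, 50 kg | 0.98–1.00 | 0.93–1.00 | none |
| Age 35, 60 kg | none | none | none |

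For the last woman the band would start at 1.17 (f = 0.80), 1.24 (0.85) or 1.31 (0.90) mg/dL, so she is not affected at a ULN of 1.1 either. With ULN 1.0 and f = 0.85 the band vanishes above a weight of 4320 / (0.85 × (140 − age)): 48 kg at age 35, 56 kg at age 50, 64 kg at age 60.

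In the Step 1 simulation, with f = 0.85, about 1% to 7% of women fell in the band. If 20% to 30% of the 200 participants were women (assumed), that is about 0.5 to 4 people.

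**Step 4: does a later check catch them?** Sections 5.6 and 6.6.3 print no formula, so the natural reading is that they use the one in 3.2; a woman printed at 60 or more then passes there too. Section 6.6.2 acts on change from her own starting value: "For creatinine elevations >1.5-fold above baseline creatinine (at screening), serum creatinine will be repeated as soon as possible". Appendix I schedules creatinine and clearance at Enrollment only.

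**The case against.** The strongest reply is that the inversion corrects itself in practice. Applied literally, it would bar nearly everyone with normal kidneys and the trial could hardly recruit 200 people. Sections 5.2 and 6.6.3 settle the direction, and Section 5.0 binds providers to the health ministry's requirements for starting the drug. Staff will probably apply the criterion as intended. That stands as a comment on likely conduct. It does not make the printed rule right, and an eligibility criterion should not depend on readers reversing it.

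On the formula, the factor, its range and the ULN all come from outside the protocol, and the group is small. That also stands, and is why this part is minor. Sites may already apply the factor through guidelines or SOPs not shown here. History review, the staff-opinion exclusion and the rule that "The site clinician has the discretion to hold FTC/TDF at any time" remain as safeguards.

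A reader might infer two stronger points, and the protocol supports neither:

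- That 3.2 admits women whom 6.6.3 would then take off drug. This needs a sex-adjusted formula in 6.6.3, and the protocol states none. On the natural reading 6.6.3 carries the same overstatement and would not catch them.
- That item 17 leaves a gap for someone with creatinine below ULN but low clearance, because its stated action refers only to an elevated level. For instance, age 50, 45 kg, creatinine 0.95 gives 4050 / (72 × 0.95) = 59.2 on the printed formula. But item 17 calculates clearance to check eligibility, and 6.6.3 stops drug temporarily for any estimated clearance below 60, without limiting this to follow-up results. What is missing is at most a cross-reference.

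**Conclusion.** The renal criterion is wrong as written and should be corrected. This rests on the protocol's text alone and needs no assumption. Its reach on a literal reading is complete, since the bullet sorts everyone the wrong way. Its practical effect is probably limited, because the intended direction is clear from other sections.

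The missing female factor is real but secondary. Its size depends on the assumed factor and ULN. It concerns mainly lighter or older women with creatinine near the ULN, and the number cannot be computed from the protocol. Alone it would be a minor correction. Neither fault touches the primary analysis.

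**What to change.** 1. In Section 3.2, reword the bullet to exclude serum creatinine at or above ULN, **or** calculated clearance below 60 mL/min. The joining word must change with the inequalities: reversing both but keeping the conjunction would exclude only people who fail both. Moving the bullet unchanged to Section 3.1 serves equally well.
2. Add a multiplier of 0.85 for women to the printed formula.
3. State in Sections 5.6 and 6.6.3 that clearance is calculated with this corrected formula.
4. Optional: refer from Section 5.2 item 17 to Section 6.6.3.

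The 60 mL/min limit stays. The cost is a few lines of protocol text, plus a check of any screening form copied from 3.2, with no new test or visit. The downside is that a few more women will stop drug, fail screening or need a repeat test.
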